Dietary intake is a modifiable factor that seems to have an important role in skeletal muscle maintenance. It has been suggested that cancer patients may experience an anabolic resistance to protein stimuli, however protein synthesis is not completely blunted and may be responsive to an elevated protein intake. In fact, recent studies demonstrated that whey protein supplementation improved protein synthesis (Deutz, et al., 2011) and walking capacity (Gillis, et al., 2016) in cancer patients. Besides protein intake, the role of fat intake remains to be established. Most studies have focused on the effect of polyunsaturated fat intake, namely

n-3 polyunsaturated fatty acids which have demonstrated a beneficial effect in the treatment of age-related sarcopenia (Henderson, 2015) and cancer associated muscle wasting (Deutz, et al., 2011). However, in a study with cancer patients with advanced disease, fish oil was compared with olive oil as placebo and no difference was found (Bruera, et al.). It is also worth pointing out that dietary patterns may be more relevant than a single nutrient intake, and interestingly in a study conducted with older adults higher adhesion to Mediterranean diet (high intake of fruit, vegetables, olive oil, nuts, fish) was associated with a lower odds of sarcopenia (Hashemi, et al., 2015).

Exercise has been recently associated with improved functional capacity and better patient reported outcomes (quality of life and psychological outcomes) in cancer patients (Jones and Alfano 2013, Manja Idorna 2016). Although, only few studies have been conducted, there is already some evidence that exercise may improve functional capacity in several settings namely breast cancer patients receiving chemotherapy/radiotherapy (Jones and Alfano 2013), pre-surgery lung cancer (Jones and Alfano 2013) and incurable advanced disease (Oldervoll, Loge et al. 2011). In addition, operated breast cancer patients receiving adjuvant chemotherapy assigned to supervised resistance training were more likely to complete treatment (Jones and Alfano 2013). Still, there is limited information regarding the effect of exercise on body composition and outcomes such as post-operative complications, chemotherapy (ChT) response and toxicity.

It has also been hypothesized that exercise may inhibit tumor growth directly. In a recent experimental study, tumor bearing mice randomized to wheel running, showed a 60% reduction in tumor incidence across five different tumor models (Pedersen, et al.). Also, NK cell infiltration was significantly increased in tumors from running mice. Mechanistic analysis showed that NK cells were mobilized by epinephrine released during exercise, which resulted in a selective mobilization of IL-6 sensitive NK cells into the tumor. Another consequence of this mobilization of NK and other T cells, is to eventually sensitize and prime it to immunotherapy (Pedersen B. K., 2011).

Although an adequate dietary intake and exercise are suggested to improve body composition which may influence outcome, reported adherence to behavioral interventions has been showed to vary substantially. In a study that focused on evaluating the impact of exercise during and after treatments of recruited cancer patients from Radiation Oncology and Gynaecology department, adhesion to 3 and 6 month program of exercise was 93 and 91%, respectively (Grabenbauer, Grabenbauer, Lengenfelder, Grabenbauer, & Distel, 2016). Another

study aiming to explore the feasibility of dietary intervention focusing on a low-fat and high fruit and vegetable intake combined with moderate exercise in breast cancer patients, also found a high adherence (75%). However, according to a meta-analysis aiming at assessing adherence of colorectal adenoma patients to behavioral interventions such as diet and physical activity, a wide range of adherence was reported, 8 to 86 % and 13 to 47 %, respectively (McMahon, et al., 2015). Furthermore, in a feasibility study of exercise and diet interventions in pancreatic and lung cancer patients a suboptimal adhesion was reported, for exercise (60%), but especially for nutritional supplements (48%) (Solheim, et al., 2017).

Bearing in mind that adherence may be a limiting factor for randomized controlled trials investigating the effect of behavioral interventions, the purpose of our study is to conduct a study to investigate adherence of upper GI cancer patients to a combined exercise and dietary intervention.

General Aims:

- To study the adherence of upper GI cancer pts to a Combined Exercise and Diet Intervention (CEDI) during neoadjuvant chemotherapy.

Specific Aims:

- To determine the rate of completion of CEDI protocol.
- To analyze the proportion of participants which achieve $\geq 50\%$ of dietary and exercise goals.
- To explore the effect of CEDI on ChT toxicity and post-op complications

Study design:

- Open label randomized controlled trial

Patient recruitment:

Recruitment will be conducted at the Oncology center of Hospital Beatriz Ângelo and patient selection will be done during the weekly multidisciplinary meeting. Patients will be enrolled at diagnosis of upper GI cancer, namely esophagus, gastric and pancreatic, provided that they are eligible for neoadjuvant ChT and with age higher than 18 years and lower than 80 years. Sample size per group was calculated bearing in mind that according to data from the World Health Organization, 14% of Portuguese adults are compliant to moderate exercise, and in our study adherence will be set as a compliance higher than 50%. Considering a power of 0.80 and an α set at 0.05, 25 patients will be needed per group. Stratified block randomization will be

conducted to allocate 25 patients to standard care and 25 to CEDI. Stratification will be performed according to disease location. Randomization will be undertaken by a randomization list created by a web based randomization system.

Methods:

- ***Clinical data:***

Demographic data such as age, sex, education level, drinking and smoking habits, and clinical data as tumor site and histological type, ChT regimens, response and toxicity, will be retrieved from electronic records. Adverse effects will also be recorded, namely ChT toxicity graded according to NCI Common Toxicity Criteria, and post -operative complications with Clavien Dindo classification.

- ***Patient Generated Subjective Global Assessment (PG-SGA)***

PG-SGA is known to be an accurate tool for the identification of malnourished cancer patients (Ottery F. , 1996) (Ottery F. , 1994). In our study, PG-SGA assessment will be conducted by an experienced dietitian and patients will be classified as well nourished (SGA A), moderately or suspected of being malnourished (SGA B) or severely malnourished (SGA C).

- ***Anthropometric measures (AM):***

AM have been used consistently due to their non-invasive feature, portability, and low cost (Rosa G, 2008). AM such as weight and height will be obtained, and Body Mass Index will be calculated. All AM will be conducted according to previously established protocols (Rosa G, 2008).

- ***Body composition assessment***

Body composition analysis will be conducted with CT scan image analysis. This technique is feasible since it is part of the clinical workup CD and GI cancer patients. CT methodology is highly precise to quantify specific tissues and to predict whole-body composition (Mourtzakis, Prado, Lieffers, Reiman, McCargar, & Baracos, 2008). Images will be acquired by Radiologists at the 3rd lumbar vertebra (L3) and processed with a specific software which performs a automatic segmentation of tissue cross-sectional areas. Manual corrections will be conducted by Radiologists, as necessary. Segmentation of tissue cross-sectional areas will be conducted according to the following Hounsfield unit (UH) thresholds: -29 to 150 for skeletal muscle, -190 to -30 for subcutaneous and intra-muscular adipose tissue and -50 to -150 for visceral

adipose tissue. Cross-sectional skeletal muscle, visceral fat and subcutaneous fat will be recorded in cm² and mean muscle radiation attenuation in HU. Skeletal Muscle Index (SMI-cm²/height²) will also be calculated. Gender specific cut-offs for SMI will be used to define sarcopenia (Martin, et al., 2013).

BIA will also be performed since it is an objective, easy, portable and non-invasive technique (Kyle, et al., 2004). Several studies have used this methodology, and in particular phase angle has been investigated as a potential nutritional indicator (Gupta, et al., 2008). BIA will be performed using a bioelectrical impedance analyzer with dual frequency (5 and 50 kHz-Bodystat 1500 MDD, Bodystat Ltd, British Isles). BIA will be conducted with patients lying in a supine position with both hand and foot not touching the rest of the body. Measurements were taken on the right side of the body. Fat Free Mass, body fat, total body water, phase angle were recorded as well as raw data such as resistance and reactance.

- ***Dietary Intake assessment***

Dietary intake will be assessed with a Food frequency questionnaire and 24 recalls using a modified USDA five-pass method at diagnosis and every visit until surgery. The Semi-quantitative Food Frequency Questionnaire that will be used, was developed for the Portuguese population (Lopes, Aro, Azevedo, Ramos, & Barros, 2007) and is designed to evaluate usual dietary intake. This questionnaire includes 86 commonly-eaten food or drinks and participants were asked to estimate the amount and frequency of intake of each food/drink according to frequency and amount. Conversion of foodstuffs to nutrients will be conducted with software Food Processor Plus (ESHA Research, Salem, Oregon) which has been adapted to the Portuguese commonly-eaten food or drinks.

The 24h recall using a modified USDA five-pass method consists in 5 steps, the first is to list all foods consumed on the previous 24h. On the second step the interviewer asks about possible forgotten food items. In the third step the interviewer clarifies the time and occasion of the consumed foods. On the fourth step subject answers to standardized questions and clarifies portion size. In the last fifth step the interviewer seeks to obtain any additional information related to the foods consumed (Johnson & K, 2002). Conversion of foodstuffs to nutrients will be conducted with Sanut software which has been developed for the Portuguese population.

- ***Functional status assessment***

Performance Status will be assessed with Eastern Cooperative Oncology Group Performance Status scale (Oken, et al., 1982). According to these criteria patients are classified from grade 0

(fully active) to grade 4 (bedridden). Prior to initiation of ChT and before surgery, data on oxygen-consumption, optimum aerobic heart rate and ECG-recordings as well as 6 min walk test will be conducted. Also, hand held dynamometer assessing grip strength will be obtained. .

- ***Physical activity***

Physical activity will be assessed with the International Physical Activity questionnaire (Craig, Marshall, Sjostrom, Bauman, Booth, & Ainsworth, 2003). This questionnaire has been validated in several countries including Portugal, and is known to be a valid and reliable tool. Participants will be categorized has having a low, moderate or high physical activity according to the frequency, duration and intensity of physical activity on the previous seven days.

- ***Patient Reported Outcome Measures(PROMs)***

Quality of life questionnaires from the European Organization for Research and Treatment of Cancer (EORTC), specifically gastric, esophagus and pancreas modules, which have already been validated for the Portuguese population, will be used to asses Patient Reported Outcome Measures at the end of Chemotherapy treatment.

- ***Intervention arm-Combined Dietary and Exercise Intervention in the***

The intervention group will receive a supervised combined moderate aerobic and resistance training, once per week with duration of 40-60 min plus daily home exercise The exercise program will be planned by an exercise physiologist aiming at personalization of exercise according to patient's age and functional capacity.

Besides exercise, intervention group will receive a one-on-one nutritional counseling, by a Dietitian. In the first visit the dietary plan will be designed and oral nutritional supplements (Forticare®, Nutricia) will be recommended to meet 1.5g of protein/kg. Patients will be recommended to take one of the supplements after exercise. Also, in order to meet a calorie intake of 30kcal/kg, patients will be recommended to maintain a fat intake of 30% of total daily calories, where 20% will be supplied by olive oil. Written materials will be given to patients and caregivers, namely a dietary plan, standard menus, recipes, and standard portions information. Follow up visits will take place every time the patient is at the hospital to receive ChT .

Patients will be recommended to maintain the dietary plan and exercise during the whole ChT treatment plan. However, due to possible symptoms after ChT, namely nausea and vomitings, patients will be asked to intensify compliance on the week preceding ChT when there is a higher probability that patients are symptom free. Patients will be contacted twice a week by phone call or interview to provide motivation support and to assess if any diet or exercise

adjustment is needed in order to maximize adherence. Also an adhesion record will be provided to the patient for monitoring of adhesion to protein, olive oil, water, supplements intake as well as home exercise.

- ***Control arm- Standard care:***

Patients allocated to the control arm will receive standard care, in which patients will be referred to the dietitian only when the clinician feels there is a need for a dietary review. Whenever relevant, exercise will be recommended but without a personalized training program, which is our current practice.

- ***Adherence Assessment***

The primary outcome will be intervention adherence, in which patients consenting to engage in the intervention protocol will be evaluated. As a secondary outcome, we will assess to what extent participants achieve their dietary and exercise goals. Participants will be considered as adherent if they have met $\geq 50\%$ of their diet and exercise goals on the week preceding ChT. Also, follow up rates will be recorded, as well as comments on burden and acceptability of the intervention. Dropout rates and reasons for leaving the study will also be recorded. Contamination of the control arm will also be analyzed. Patients will be contacted every week by phone call or interview to assess adherence.

Statistical analysis:

Statistical analysis will be conducted for the primary and secondary outcome with an intention to treat and per protocol approach, respectively. Continuous variables will be described as mean, median and range, while categorical variables will be expressed as frequency and percentage. Differences in mean continuous variables will be analyzed by t-test or Mann Whitney U test as appropriate, according to variable's adjustment to a normal distribution. Shapiro-Wilk test will be used to test normality. Pearson or Spearman correlation analysis will be performed as appropriate to assess the association between continuous variables. Chi square test of independence or Fisher exact test will be used to assess the association between categorical variables.

Ethics:

The study protocol has been approved by the Scientific and Ethics Committee of Hospital Beatriz Ângelo in Loures, Portugal. Informed consent will be obtained from every patient.

Clinical data will be prospectively collected from electronic charts, however data will be coded in order to maintain anonymity.

References:

Bruera, E., Strasser, F., Palmer, J., Willey, J., Calder, K., Amyotte, G., et al. (s.d.). Effect of Fish Oil on Appetite and Other Symptoms in Patients With Advanced Cancer and Anorexia/Cachexia: A Double-Blind, Placebo-Controlled Study. *Journal of Clinical Oncology*, 21(1), 129-134.

Chu, M. P., Lieffers, J., Ghosh, S., Belch, A., Chua, N. S., Fontaine, A., et al. (2017). Skeletal muscle density is an independent predictor of diffuse large B-cell lymphoma outcomes treated with rituximab-based chemoimmunotherapy. *Journal of Cachexia, Sarcopenia and Muscle*, 8(2), 298-304.

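### No planned, systematic count of harms outside chemotherapy toxicity and surgical complications, although most of the exercise under test is done unsupervised at home

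*Combined protocol and SAP*

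**What the plan says.** The Clinical data paragraph under Methods lists two kinds of adverse effect: "Adverse effects will also be recorded, namely ChT toxicity graded according to NCI Common Toxicity Criteria", and "post -operative complications with Clavien Dindo classification". The one specific aim that bears on safety covers the same two: "To explore the effect of CEDI on ChT toxicity and post-op complications". The source for toxicity is the chart: "ChT regimens, response and toxicity, will be retrieved from electronic records".

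The Intervention arm section describes what is being tested. Exercise is supervised "once per week with duration of 40-60 min plus daily home exercise". On the dietary side, "oral nutritional supplements (Forticare®, Nutricia) will be recommended to meet 1.5g of protein/kg".

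Other provisions come close to harms without being designed to collect them:
- Twice-weekly contacts, described under the intervention arm only, give motivation and serve "to assess if any diet or exercise" adjustment is needed.
- The patient's own record tracks intake of protein, oil, water and supplements, and home exercise.
- Adherence Assessment adds remarks on burden and acceptability, a weekly contact about adherence, and this: "Dropout rates and reasons for leaving the study will also be recorded".
- ECG and walking tests are done before chemotherapy and before surgery, as functional assessments.

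The Statistical analysis section has no safety analysis.

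**The concern.** The components under test are aerobic and resistance training and an oral supplement, given during chemotherapy to patients up to almost 80 years old, some of whom may be malnourished. The foreseeable harms of those components include a strain, a fall, a cardiac or syncopal event around a session, and intolerance of the supplement. Neither listed category is built to capture them. A patient who falls during home exercise, misses some sessions and stays in the study has an event with no planned place in the data. Hospital charts may not record it.

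Two things are at stake. First, a report that describes the intervention as acceptable would have no systematic count of harm beside that statement, and no reports could be mistaken for no events. Second, where an injury or intolerance lowers adherence in a patient who stays in, the plan has no systematic way to show it. That matters to anyone deciding whether to take CEDI into a larger trial.

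**Working it through.** **1. Where each kind of event would be recorded under the plan as written.**
- Chemotherapy toxicity: Clinical data; graded (NCI), both arms, from electronic records.
- Surgical complication: Clinical data; graded (Clavien-Dindo), both arms.
- Gastrointestinal reaction to the supplement: probably graded as chemotherapy toxicity, since the symptoms overlap with the nausea and vomiting that the Intervention arm section expects after chemotherapy. It would be counted, but under another label.
- Exercise injury, fall, cardiac or syncopal event that leads to dropout: reason for leaving.
- The same event without dropout: at most a remark on burden, or something mentioned in a call about adjusting the programme. There is no planned question, grade or table.

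The gap is therefore mainly the last line, plus supplement intolerance that is not graded as toxicity.

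**2. Share of sessions that are unsupervised.** The Intervention arm section gives one supervised session a week plus daily home exercise.
- Seven home sessions in addition to the supervised one: 7 / (7 + 1) = 0.875.
- Supervised session replaces that day's home session: 6 / (6 + 1) = 0.857.

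This is a share of sessions, not of minutes; the length of a home session is not given.

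**3. The denominator.** Patient recruitment gives 25 per group, from 14% compliance, power 0.80 and α 0.05. Two assumptions are needed to reproduce it: an intervention rate of 50%, which the text may intend as a per-patient threshold, and a two-sided test.
- Arcsine formula: h = 2·asin(√0.50) − 2·asin(√0.14) = 0.804; n = 2(1.960 + 0.842)² / h² = 24.3, rounded up to 25.
- Pooled normal formula: 26, with power 79.8% at 25.

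So 25 reproduces. It is an adherence calculation and the present point does not depend on it.

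**4. What 25 patients per arm could say if harms were collected and none occurred.**
- One-sided 95% upper bound: 1 − 0.05^(1/25) = 0.113.
- Upper limit of a two-sided 95% interval: 1 − 0.025^(1/25) = 0.137.

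**5. Chance of seeing at least one event in 25 patients, 1 − (1 − p)^25.** The documents give no event rates, so p is an assumption.
- p = 1%: 22%
- p = 2%: 40%
- p = 5%: 72%
- p = 10%: 93%

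Systematic collection would reveal common harms and would often miss rare ones. Without it even the 11% bound is unavailable, because an absence of reports cannot be read as an absence of events.

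**The case against.** The strongest reply is that this is an adherence study. No aim claims to establish safety, and 25 patients could not establish it anyway (steps 4 and 5). That stands, and it limits what the added data can be asked to do. It does not explain why two categories of harm are recorded and those closest to the intervention are not.

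A reader might infer more than the documents support, in four ways:
- *That the trial yields no safety information.* It does yield some. A between-arm difference in toxicity or surgical complications would reflect CEDI whatever cause a clinician assigned, and gastrointestinal effects of the supplement would probably be in that count.
- *That intervention harms cannot appear at all.* They can, through dropout reasons, remarks on burden, adjustment calls or charts. The appearance is unsystematic, and part of that machinery is described only for CEDI patients.
- *That the trial fails its own question because injury cannot be separated from lack of motivation.* The stated aims are the completion rate and the proportion reaching at least half of their goals, not the causes of non-adherence. The contacts could also bring an injury to light.
- *That 86% to 87.5% of harms would be missed.* The figure is the share of unsupervised sessions. It does not measure missed events.

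The word *namely* may also not close the list: the Intervention arm section uses it before what look like examples of symptoms. Even on the open reading, no other category is named anywhere and none has a collection method.

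**Conclusion.** The point holds in a limited form. The plan names two categories of adverse effect and sets out no systematic collection of harms outside them, chiefly exercise injuries, falls, cardiac or syncopal events and supplement intolerance, while about 6 of 7 or 7 of 8 exercise sessions are unsupervised. Such events would be found only by chance, so the trial has no planned count of harms of the intervention itself. The existing randomised comparison remains useful as partial, indirect evidence.

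How many events would be missed cannot be estimated from the documents. The conclusion rests on reading the protocol text as complete on this point. It does not affect the sample size or the adherence outcomes.

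**What to change.** Add a third category to the Clinical data list: other adverse events, meaning injury, fall, cardiac or syncopal event, supplement intolerance and any serious adverse event.

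- **Ascertainment.** Ask one fixed question at the same frequency in both arms, for example at the weekly contact in Adherence Assessment (stating that it covers both arms) or at chemotherapy visits. Do not rely on the twice-weekly CEDI contacts. Falls, syncope and nausea also occur on chemotherapy alone, so a count in one arm has no comparator, and more frequent asking in one arm would create a difference.
- **Grading.** Use the NCI scale already in the plan.
- **For CEDI patients, in addition.** Record whether the event occurred during or after a session or supplement intake, and whether it changed adherence.
- **Reporting.** Give the number of patients with at least one event by arm, descriptively, with the exact upper bound where the count is zero.
- **Protecting the toxicity comparison.** Keep every gastrointestinal and other toxicity event in the between-arm chemotherapy toxicity comparison regardless of attributed cause, even if it is also listed as supplement intolerance. Removing events on open-label attribution could occur only in the CEDI arm and would favour it.

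The cost is slightly longer contacts in both arms and one extra table. The sample size does not change. The report should say that the data describe harms and do not establish safety.

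### Dietary intake is measured repeatedly, but the plan does not say how repeated values become one between-arm comparison and makes no use of the diagnosis value

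*Combined protocol and SAP*

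**What the plan says.** The Dietary Intake assessment section of the combined protocol and SAP schedules a food frequency questionnaire and 24-hour recalls "at diagnosis and every visit until surgery". The number of visits is not given. Under the intervention arm, "Follow up visits will take place every time the patient is at the hospital to receive ChT", so the count depends on the chemotherapy a patient receives. Under the control arm, "patients will be referred to the dietitian only when the clinician feels there is a need for a dietary review"; the text does not say whether control recalls follow the same visits.

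The Statistical analysis section is one paragraph. For continuous variables: "Differences in mean continuous variables will be analyzed by t-test or Mann Whitney U test as appropriate". For associations: "Pearson or Spearman correlation analysis will be performed as appropriate to assess the association between continuous variables". For categorical data: "Chi square test of independence or Fisher exact test will be used to assess the association between categorical variables". It contains no mixed model, estimating equation, repeated-measures method, baseline adjustment, named visit or rule for summarising several values per patient.

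On the role of intake, the Adherence Assessment section states: "The primary outcome will be intervention adherence". How far participants reach their dietary and exercise goals is secondary.

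**The concern.** Recalls from one patient resemble each other, and every test listed assumes independent observations. An analyst with a file of recalls and this paragraph must decide what to feed into the t-test, and the plan does not guide that choice. If all recalls go in, the standard error is too small. If each visit is tested, there are several chances of a false positive and no stated way to choose among them. If one visit is used, the 24-hour recall comparison rests on a single day per patient, and the protocol itself expects symptoms after chemotherapy to affect compliance. The trial is open label, so a choice made after the data are seen is open to question.

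Protein and energy targets define the dietary part of the intervention, so a between-arm comparison of intake is a natural use of these data. The diagnosis value is also collected but has no stated use in the comparison.

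**Working it through.** **1. The plan's own figure.** The Patient recruitment section gives 25 per group at α = 0.05 and power 0.80. Reading the two rates as 14% and 50% (the 50% is stated as a compliance threshold, so this reading is an assumption):

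- Pooled, two-sided: n = [1.96·√(2·0.32·0.68) + 0.8416·√(0.14·0.86 + 0.50·0.50)]² / 0.36² = (1.293 + 0.512)² / 0.1296 = 25.1, so 26.
- Arcsine: h = 2·asin√0.50 − 2·asin√0.14 = 0.804; n = 2·(2.802/0.804)² = 24.3, so 25.

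The figure is reproduced. It rests on a binary adherence rate, so nothing below changes it.

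**2. Inputs for intake.** n = 25 per arm (documents). On-treatment recalls per patient, m, and within-patient correlation, ρ, are assumptions: m = 3 to 8, ρ = 0.3 to 0.5. The calculation takes equal m in both arms and a single-recall SD of 1.

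**3. Formulas.**

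- Pooling all recalls: true type I error = 2·[1 − Φ(1.96/√D)], with D = 1 + (m − 1)ρ. For m = 4, ρ = 0.3: D = 1.9, error 15.5%. For ρ = 0.5: D = 2.5, error 21.5%.
- Patient mean: variance relative to one recall, V = D/m. For m = 4: 1.9/4 = 0.475 and 2.5/4 = 0.625, so reductions of 52.5% and 37.5%.
- Visit by visit, and t-test on patient means: simulated, 20,000 trials per cell.

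| m | ρ | Pooled, type I error | Any visit significant | t-test on patient means | V |
|---|---|---|---|---|---|
| 3 | 0.3 | 12.1% | 13.8% | 5.3% | 0.533 |
| 3 | 0.5 | 16.6% | 12.6% | 5.1% | 0.667 |
| 4 | 0.3 | 15.5% | 17.4% | 5.1% | 0.475 |
| 4 | 0.5 | 21.5% | 15.6% | 5.0% | 0.625 |
| 8 | 0.3 | 26.6% | 30.4% | 4.8% | 0.387 |
| 8 | 0.5 | 35.6% | 25.9% | 5.0% | 0.562 |

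Simulation of the pooled test at m = 4 gave 16.0% and 21.8%, in line with the formula.

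**4. Power.** Power = Φ(d/√(2V/25) − 1.96). For an assumed true difference of 0.5 SD of a single recall, one recall (V = 1) gives Φ(1.768 − 1.96) = 42%. The mean of 4 gives Φ(2.236 − 1.96) = 61% at ρ = 0.5 and Φ(2.565 − 1.96) = 73% at ρ = 0.3. The difference detectable with 80% power is 2.802·√(2V/25): 0.79 SD for one recall, 0.55 to 0.63 SD for the mean of 4.

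**5. The diagnosis value.** If the diagnosis recall has the same correlation ρ with each later recall, adjusting the patient mean for it leaves variance V − ρ². For m = 4 this is 0.475 − 0.09 = 0.385 (ρ = 0.3) or 0.625 − 0.25 = 0.375 (ρ = 0.5), a further cut of 19% or 40%. If chemotherapy or the intervention weakens the link with diagnosis, the gain is smaller.

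**The case against.** The strongest reply is that the listed tests are adequate. Average each patient's recalls, compare the averages with the stated t-test, and the error rate is about 5% with no recall discarded. That is correct. A reader might infer that the plan must either inflate false positives or throw most recalls away. The documents do not support this: they nowhere say recalls will be pooled or dropped, and a valid route lies within the listed methods. What remains is that the plan does not choose that route.

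The other replies:

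- **Mean intake is not a named outcome.** This stands. The aims concern adherence, completion, goal achievement, toxicity and complications. It limits the importance of the point.
- **Intake need not underlie the contamination analysis.** This stands. The plan promises that analysis without naming a variable, so linking it to intake is inference.
- **The food frequency questionnaire covers usual intake, and patients keep an adhesion record.** This stands in part. The questionnaire softens the single-day problem but is scheduled at the same visits, so the same choice arises. The adhesion record is described only for the intervention arm.
- **A change from diagnosis would fit the t-test and use the baseline.** It would be valid, but for m = 4 its variance is V + 1 − 2ρ: 0.875 at ρ = 0.3 and 0.625 at ρ = 0.5, against 0.385 and 0.375 with adjustment.
- **The magnitudes are assumed.** This stands for recall count, correlation and effect size, hence the ranges.

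**Conclusion.** The analysis of repeated dietary intake is unspecified, and the only stated between-arm method for continuous data makes no use of the diagnosis value. The listed tests become valid once there is one value per patient, but the plan does not define that value.

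With 4 recalls and ρ of 0.3 to 0.5, the routes left open range from a valid 5% test on patient means, through a 16% to 17% chance of at least one false positive when visits are tested separately, to 15.5% to 21.5% under pooling. Using one recall keeps the error rate but, for a 0.5 SD difference, gives 42% power against 61% to 73% with the mean. These sizes describe what the plan permits, not what it will do.

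The point is an inexpensive improvement to a supporting analysis. It does not touch the primary outcome or the sample size.

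**What to change.** For any between-arm comparison of intake, add to the Statistical analysis section one analysis with one named contrast, chosen from:

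- a linear mixed model with arm, visit and diagnosis intake as fixed effects and a random intercept per patient; or
- each patient's mean over all on-treatment recalls, compared between arms by ANCOVA adjusting for diagnosis intake.

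State that individual recalls will not be entered as independent observations in t-tests or correlations. State that both arms' recalls come from the same visits, since visit timing is described only for the intervention arm. Say how missing recalls and unequal visit numbers will be handled.

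The cost is a few sentences and a standard model on data already planned; if controls would not otherwise be seen at those visits, their recalls must be scheduled. Each option has a small downside. The mixed model assumes missing recalls are explained by the observed data. The patient mean gives equal weight to patients with few and many recalls, so the two options are close but not identical when counts differ.
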